**Exclusion Criteria**

1. History of active liver disease.
2. Pregnant or lactating women are ineligible due to unforeseeable risks to embryo or fetus.
3. Concurrent use of any medicinal botanical, natural, or other herbal compound/s that the study PI believes could potentially have an impact on the results/objectives of this study.
4. Planned subtotal or debulking surgery, as determined by enrolling physician determination, is not permissible.
5. Prior systemic chemotherapy for oral SCC; note that prior chemotherapy for a different cancer is allowable.
6. Prior radiotherapy for oral SCC is permissible if disease free for one year since prior oral cancer treatment and free of significant late radiation effects.
7. Severe active comorbidity, such as uncontrolled cardiac disease, infection, severe COPD.

*I have reviewed all inclusion and exclusion criteria and confirm the subject is eligible.*

\_\_\_\_\_  
(CRC Signature)

\_\_\_\_\_  
(Date)

\_\_\_\_\_  
(Investigator/Enrolling Physician Signature)

\_\_\_\_\_  
(Date)

## **4.6 Discontinuation of Study Treatment, Withdrawal, and Compliance**

Discontinuation from the study treatment does not mean discontinuation from the study. Subject will be considered in follow-up, study procedures should still be completed as indicated by the study protocol, and AEs/SAEs will continue to be reported according to this protocol.

In the absence of treatment delays due to adverse events, study treatment/intervention may continue until:

- Disease progression.
- General or specific changes in the subject's condition renders the subject unacceptable for further treatment in the investigator's judgment.
- Inter-current illness that prevents further treatment administration.
- Subject decides to withdraw from the study.
- The subject has significant noncompliance with the protocol (see below).
- Unacceptable adverse event(s) and/or dose level reduction beyond requirements as detailed in this protocol.
- Study stopping rules are met.

Subjects who sign the informed consent form, enroll and receive the study intervention, but subsequently withdraw, or are withdrawn or discontinued from the study will not be replaced.

### **Consent Withdrawal**

A subject may decide to withdraw from the study at any time. MCWCC CTO will follow its IRB of record's SOPs regarding consent withdrawal.

If a subject intends on withdrawing consent, staff should confirm which of the following options the subject chooses and document the discussion:

- Full consent withdrawal, with no study follow-up.
- Selective consent withdrawal from interventional portion of the study but agree to continued follow-up of associated clinical outcome information.

### **Investigator-Initiated Withdrawal**

The investigator will withdraw a subject whenever continued participation is no longer in the subject's best interests. Reasons for withdrawing a subject include, but are not limited to, disease progression, the occurrence of an adverse event or a concurrent illness, a subject's request to end participation, a subject's noncompliance or simply significant uncertainty on the part of the investigator that continued participation is prudent. The reason for study withdrawal and the date the subject was removed from the study must be documented.

## **4.7 Lost to Follow-Up**

The following actions must be taken if a participant fails to return to the clinic for a required study visit and/or is unable to be reached for follow-up:

- The investigator or designee must make every effort to regain contact and/or reschedule a missed visit with the participant.
- A participant is deemed lost to follow-up if his/her status cannot be obtained after *all* of the following occurs at two consecutive scheduled protocol calendar timepoints:

- Three telephone calls (at least one day apart) from the study team are unanswered,

**AND**

- A letter to the participant's last known mailing address goes unanswered, **AND**
  - These contact attempts must be documented in the participant's medical record or study file.
- Update OnCore® (Follow-up tab and eCRF) when a participant is officially considered lost to follow-up.
  - If a subject is considered lost to follow-up, but subsequently contacts the study team, the subject should be considered in follow-up again.

#### **4.8 Accrual Suspension and Closure**

The MCW PI facilitates the suspension and closing of accrual in the following manner:

- OnCore® tracks accrual throughout the study.
- If the study must be suspended, OnCore® is updated to a 'suspended' status.
- When the accrual number is reached, OnCore® notifies staff of study closure.

#### **4.9 End of Study Definition**

A participant is considered to have completed the study if he or she completed all phases of the study, including the last visit or the last scheduled procedure shown in the calendar of events or has been discontinued.

#### **4.10 Study Discontinuation and Closure**

This study may be temporarily suspended or prematurely terminated if there is sufficient reasonable cause (as determined by the MCW study PI, DSMC, sponsor, and/or IRB). Written notification, documenting the reason for study suspension or termination, will be provided by the suspending or terminating party to study participants, investigator, funding agency, the Investigational New Drug (IND) sponsor and regulatory authorities. If the study is prematurely terminated or suspended, the MCW principal investigator (PI) will promptly inform the MCW Institutional Review Board (IRB), and the sponsor and will provide the reason(s) for the termination or suspension. Study participants will be contacted, as applicable, and be informed of changes.

## 5 TREATMENT PLAN

### 5.1 ATB Administration

ATB will be administered on an outpatient basis. ATB will be administered at a dose of 1,200 mg three times per day (roughly spaced every eight hours) as has been studied for ATB in human oral leukoplakia trials and in esophageal cancer prevention trials. ATB may be taken with or without food.

Regimen Description					
Study agent	Premedication; precautions	Dose	Route	Schedule	Duration
ATB	None	1,200 mg, Three times a day	Oral	Daily	7-28 days a
a. Total duration depends upon scheduling of surgery. ATB administration must not exceed 28 days.					

- There will only be ONE ATB dose on day 1. Dose on Day 2 must be delayed until completion of PK specimen (blood and saliva) collection.
- Patient must submit completed study dairy to the study coordinator.

### 5.2 Supply

ATB will be produced by National Traditional Chinese Medicine Pharmaceutical Engineering Technology Research Center and shipped to MCW in the form of a tablet. ATB will be stored at room temperature in a cool place, free from excessive moisture and should be stable for two years. Analysis of pharmacokinetic properties is necessary before future efficacy trials can be initiated. We will examine an oral ATB dose of 1,200 mg, three times per day.

Study agent will be shipped to MCW in one batch. Study agent ordering contact information:

**[name].**  
**Department of Pharmacological and Pharmaceutical Sciences**  
**College of Pharmacy**  
**[name]**  
**University of Houston**  
**[name]**  
**Contact Information: [contact]**

Each patient-specific bottle will be labeled by IDS pharmacy with the following:

- The study number;
- The bottle number (i.e., Bottle 1 of 2 and Bottle 2 of 2);

- The number of tablets;
- The patient ID number (e.g. ATB-YYY, where the study number and sequence number represent the unique patient identifier assigned at registration);
- The patient's initials (i.e., first, middle, last);
- A blank line for the site pharmacist to enter the patient's name;
- Administration instructions (i.e., "Take xx tablets every day for xx days");
- Storage instructions (i.e., "Store at controlled room temperature, xx degrees");
- Emergency contact instructions.

### **5.3 Storage and stability**

The intact bottles should be stored at controlled room temperature (15°C – 30°C). Shelf life surveillance studies of the intact bottle are ongoing. Current data indicate ATB is stable at 90 days without decrement of active components at controlled room temperature (15°C – 30°C).

### **5.4 Accountability**

The investigator, or a responsible party designated by the investigator, must maintain a careful record of the inventory and disposition of all agents. It is the responsibility of the investigator to ensure that the agents are only dispensed to study patients.

### **5.5 Drug Destruction**

Opened bottles of ATB must be disposed of by incineration at the site as chemotherapy or biohazardous waste. At the completion of the study, all unused ATB also must be incinerated at the site. It is the responsibility of the investigator to ensure that a current record of agent disposition is maintained at each study site where agents are inventoried and disposed, including dates and quantities.

### **5.6 Biopsy specimen, Operative Specimen, and Tissue Processing**

Tumor specimens will be analyzed for ATB accumulation and stored for tissue banking for future research. Submission of a block is preferred and is highly encouraged. If a block is not available, please provide at least five unstained slides. The block (or unstained slides) should be hand delivered to the CRI Histology Core (address below): The contact person is [name] ([contact]).

Second post-ATB administration tumor biopsy is not needed because the OR-resected tumor will serve this purpose. At the time of surgery, a portion of the resected tumor will be utilized for the study.

The resected tumor will be received and processed by the MCW tissue bank staff. The tissue will be fixed in 10% buffered formalin as soon as resected, grossed into cassettes and processed into paraffin blocks. Once the blocks are in paraffin – the blocks will be delivered to the CRI Histology Core for further testing. The paraffin block of the resected tumor and biopsy should be delivered to the following location:

Children's Research Institute – Histology Core Laboratory  
Medical College of Wisconsin

[name]  
 [name]  
 [name]

The biopsy specimen and tumor specimen will be used for PK analysis.

### 5.7 Dose Modifications

As indicated in the study calendar, a complete metabolic panel (including LFTs) will be performed mid-way during the course of ATB. Adverse events will be graded according to CTCAE v.5.

Adverse Event (CTCAE, v. 5)	Action
Non-hematological, grade 1 or 2	Continue ATB therapy at full dose prescribed. Apply maximum supportive care recommendations. If persistent duration of grade 2 adverse event is affecting quality of life, a one-time decrease of 25%.
Non-hematological, grade 3 or 4	
Apply maximum supportive care recommendations. Hold ATB therapy until recovery to grade <math>\leq 1</math> (up to 7 days).
 
If concomitant elevation of AST/ALT 3 times the upper limit of normal and bilirubin elevation 2 times the upper limit of normal (Hy's Law criteria) the patient must be removed from study treatment, ATB must be permanently discontinued.
 
If recurrence of adverse event after drug hold and/or interruptions is observed and maximum supportive care measures applied, a dose reduction by 25% is recommended. ATB should not be used at doses below 50%

Non-hematological, grade 3 or 4 and adverse events NOT resolved to grade $\leq 2$ within a maximum of 14 calendar days from last planned administration	Dose reductions by 25% (up to 2 reductions) will be considered after maximum supportive care recommendations are introduced.

Dose Level	Dose
-2	600 mg TID
-1	900 mg TID
0	1200 mg TID

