10. Patient will complete study diary (Appendix 2) with all relevant information and will submit the diary to study coordinator.
11. Study coordinator will contact patients twice weekly for compliance assessment and reminders for protocol procedures.
12. Chemistry panel with AST, ALT, T. Bilirubin will be performed approximately midway during treatment.
13. The indicated assessment for this timepoint will be collected only once with a window of 2 days: Day -2 to Day -1 of surgery.

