## 3 STUDY DESIGN

### 3.1 General Description

A window of opportunity (WOO) clinical trial permits examination of effects of study agent on cancer patients during the “window” between diagnosis of their cancer and their definitive cancer surgery. Similar to the phase 0 study design, the WOO trial design permits examination of the biologic effects of a study agent; in this trial we will examine PK properties of ATB.

Blood samples will be taken at the following time points Day 1: Blood samples will be taken at baseline (prior to study agent administration), then at 30, 60, 120, 180, 240, 360, 480, and 1,440 min (a total of nine points). For each blood draw 1 ml of blood will be drawn to yield approximately 500 µl or 0.5 ml of plasma. All blood sample collections are allowed a window of  $\pm$  10 minutes. A blood sample for liver function test will be performed following completion of ATB on day -1 or day of surgery.

Saliva samples (2-4 ml) will be collected at the following time points: Day 1: Predose, then at 30, 60, 120, 180, 240, 360, 480, and 1440 min (a total of 9 points). A  $\pm$  5 minute window is allowed for the 30 min time point. All other time points will have a  $\pm$  10 min window. However every effort should be made to obtain samples at the precise time. Day 2 to day -1 of surgery: A total of at least three patient samples (saliva) will be collected for each time point (predose, before lunch, or before dinner). Participants have no limitation on eating or drinking prior to saliva sample collection. Saliva samples will be collected in a 5 ml bio vial and then frozen and stored in an airtight container at 0 to -20° C until batch shipment to [name] laboratory at the University of Houston. The blood, saliva, and tumor tissue specimen will be used for PK analysis and should be shipped in dry ice to the following location:

[name]  
Department of Pharmacological and Pharmaceutical Sciences  
College of Pharmacy  
[name]  
University of Houston  
[name]  
Contact Information: [contact]

Participants will continue ATB administration for a total of seven to 28 days, which they will record in a study diary (Appendix 2). ATB administration must not exceed more than 28 days. The study diary will be collected at the completion of the study.

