#### Inclusion Criteria

1. Clinical diagnosis of oral cavity squamous cell cancer.
2. Patient can start study agent administration but histological confirmation of squamous cell cancer (SCC) of the oral cavity (or histologic variants of SCC) by the pathologist must happen within seven days of registration in order to continue study agent administration.
3. Clinical stage II-IVA (as defined by the AJCC, 8th Edition) and amenable to surgical resection
4. New diagnosis of oral SCC, new second primary, or recurrent oral SCC following a minimum remission of six months following previous definite surgery.
5. History and physical examination by an otolaryngologist and medical oncologist within 14 calendar days of study registration.
6. Study agent administration should start within seven days of registration.
7. Patient must receive administration of study agent for a minimum of seven days.
8. ECOG Performance status  $\leq 2$ .
9. Age  $\geq 18$  years.
10. CBC/differential obtained within 14 calendar days prior to registration, with adequate bone marrow function defined as follows:  
Absolute neutrophil count (ANC)  $\geq 1,500$  cells/mm^3;  
Platelets  $\geq 100,000$  cells/mm^3;  
Hemoglobin  $\geq 8.0$  g/dl (Note: The use of transfusion or other intervention to achieve Hgb  $\geq 8.0$  g/dl is acceptable.);
11. Adequate renal and hepatic function within 14 calendar days prior to registration, defined as follows:  
Serum creatinine  $< 1.5$  mg/dl or creatinine clearance (CrCl)  $\geq 50$  ml/min within 14 calendar days prior to registration, determined by 24-hour collection or estimated by Cockcroft-Gault formula:  
CrCl male =  $[(140 - \text{age}) \times (\text{wt. in kg})] / [(\text{Serum Cr mg/dl}) \times (72)]$   
CrCl female =  $0.85 \times (\text{CrCl male})$

CRC Initials: \_\_\_\_\_

Date: \_\_\_\_\_

Investigator/Enrolling Physician Initials: \_\_\_\_\_

Date: \_\_\_\_\_

Subject Initials: \_\_\_\_\_ Subject Study ID: \_\_\_\_\_ Enrolling Physician \_\_\_\_\_

12. Total bilirubin < 2 x the institutional ULN within 14 calendar days prior to registration.
13. AST or ALT  $\leq$  3 x the institutional ULN within 14 calendar days prior to registration.
14. Magnesium, calcium, glucose, potassium, and sodium within 14 calendar days prior to registration, with the following required parameters:
  - Magnesium: > 0.9 mg/dl or < 3 mg/dl;
  - Calcium: > 7 mg/dl or < 12.5 mg/dl;
  - Glucose: > 40 mg/dl or < 250 mg/dl;

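### Section 5.7 prints the mandatory liver stop, set by ULN multiples, only in the grade 3-4 cell, and nothing says it overrides the grade 1-2 instruction to continue at full dose

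*Combined protocol and SAP*

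**What the plan says.** The Section 5.7 table has three rows, all for non-haematological events and all keyed to CTCAE v5 grade.

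- **Grade 1 or 2:** "Continue ATB therapy at full dose prescribed", with supportive care. The only relief is a single 25% reduction for a persistent grade 2 event that affects quality of life.
- **Grade 3 or 4:** the action cell has three paragraphs. The first holds ATB until recovery. The second is the liver rule: "If concomitant elevation of AST/ALT 3 times the upper limit of normal and bilirubin elevation 2 times the upper limit of normal", a combination the protocol labels Hy's Law, then "the patient must be removed from study treatment, ATB must be permanently discontinued". The third covers recurrence and 25% reductions.
- **Grade 3 or 4, unresolved:** up to two 25% reductions are to be considered.

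Three other places bear on the rule. The inclusion criteria admit patients with "Total bilirubin < 2 x the institutional ULN within 14 calendar days prior to registration" and with AST or ALT up to "3 x the institutional ULN within 14 calendar days prior to registration". Study Calendar footnote 12 states "Chemistry panel with AST, ALT, T. Bilirubin will be performed approximately midway during treatment". Section 3.1 adds, for day -1 or the day of surgery, "A blood sample for liver function test will be performed following completion of ATB".

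**The concern.** The table uses two scales. Grade decides which row the investigator reads; ULN multiples decide whether the liver stop is met. Because the stop sits inside one grade row, a reader who works by row reaches it only after classing the event as grade 3 or 4. A patient whose two liver results meet the stop but are both graded 2, with no other grade 3-4 event, falls in the row that says to carry on at full dose.

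This is the protocol's only mandatory liver stop, so its reach should not depend on the row consulted. Section 1.1 gives some reason for care: the largest earlier study reported jaundice in a small, unquantified number of patients. No rate or attribution is given, so this shows relevance and not likelihood.

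The rule would mainly be applied at the mid-course panel. If midway means half of a 7 to 28 day course, 7/2 = 3.5 to 28/2 = 14 days of dosing would remain. The next scheduled liver panel falls at Day -2 to Day -1 of surgery (calendar footnote 13), near the end of dosing.

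**Working it through.** The plan gives no figure to reproduce. The check has two parts: whether any text settles the precedence, and when the two rows would conflict.

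**1. Is precedence stated anywhere?**

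| Place | What it provides | Liver threshold or precedence? |
|---|---|---|
| 5.7, sentences above the table | Mid-course metabolic panel including liver tests; grading by CTCAE v5 | No |
| 5.7, grade 1-2 row | Continue at full dose | No exception |
| 5.7, grade 3-4 row | The liver stop | Threshold yes, precedence no |
| 5.7, unresolved grade 3-4 row | Reductions considered | No exception |
| 4.6, reasons to end treatment | Unacceptable adverse events; unspecified stopping rules | No |
| 4.6, investigator-initiated withdrawal | Best-interests judgement | No |
| 6.5, dose-limiting toxicity | Grade 3 or higher, definitely or probably related | No |

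The stop appears once, and no sentence extends it beyond its cell. Its position does not look like a fault of text extraction, because it lies between two other paragraphs of the same cell.

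**2. When do the rows conflict?**

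Inputs from Section 5.7: AST/ALT trigger 3 x ULN; bilirubin trigger 2 x ULN; both required together. Inputs not in the documents: *a*, the top of CTCAE v5 grade 2 for AST/ALT, and *b*, the same for bilirubin, both in multiples of ULN.

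A patient meets the stop with both results at grade 2 only if AST/ALT lies between 3 and *a* and bilirubin lies between 2 and *b*. That region exists only if *a* > 3 **and** *b* > 2. If either condition fails, anyone beyond both triggers already has at least one result at grade 3 or above, is in the row that holds the stop, and the placement does no harm.

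The assumed ceilings below only show the range; the sponsor can look up the actual values.

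| Assumed *a*, *b* (x ULN) | AST/ALT width, *a* - 3 | Bilirubin width, *b* - 2 | Overlap |
|---|---|---|---|
| 3, 2 | 0 | 0 | None |
| 5, 2 | 2 | 0 | None |
| 3, 3 | 0 | 1 | None |
| 4, 2.5 | 1 | 0.5 | AST/ALT 3-4 with bilirubin 2-2.5 |
| 5, 3 | 2 | 1 | AST/ALT 3-5 with bilirubin 2-3 |

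The answer changes with the assumption, so the documents alone establish a possible conflict and not a certain one. The missing precedence statement, by contrast, can be read directly from the text.

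**The case against.** The strongest reply is that the text already leans to the safe reading. The liver sentence is a complete conditional with its own trigger, a recognised label and mandatory wording; the grade 1-2 instruction is general. A specific rule normally governs a general one, and the table is introduced by a sentence about the mid-course liver tests. Most investigators who saw results meeting a printed removal rule would follow it whatever cell it was in. Section 4.6 also has the investigator withdraw a subject whose continued participation is not in their interest, and Section 8.2 requires regular review by the study team. All of this stands. It makes the harmful reading unlikely, but it replaces a mandatory rule with inference and judgement.

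It is also fair to say that the conflict turns on cut-points outside the documents, and that three of the five assumed pairs give none. That limits the finding to a conditional one.

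Three stronger readings are tempting and are not supported:

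- *The protocol keeps patients who meet the stop on drug.* It does not say so. Reading the stop as free-standing is natural; the text merely fails to require it.
- *Entry limits at the same multiples as the stop show how serious the placement is.* The distance from entry to trigger is the same wherever the rule is printed, and moving it changes nothing there. It does not measure this defect. The documents also give no frequency for patients near both limits, and "History of active liver disease" is an exclusion.
- *The mid-course panel is the last liver test before dosing ends.* The calendar has ATB given daily until Day -1 of surgery, and footnote 13 allows the later panel on Day -2, so that panel can precede the last dosing day.

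**Conclusion.** The point holds as a gap in drafting with a conditional safety consequence. It is certain from the text that the liver stop is defined in ULN multiples, is printed only in the grade 3-4 cell, and is given no stated precedence over the grade 1-2 instruction. It is conditional that a patient could meet the stop at grade 2: this requires the CTCAE v5 grade 2 ceilings to exceed 3 x ULN for AST/ALT and 2 x ULN for bilirubin, both at once.

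The importance is minor. Eight patients are planned, the course is short, the safe reading is the natural one, and the documents give no probability for the event. Sample size and the PK analysis are unaffected. The change is still worth making because it concerns a mandatory safety rule and costs almost nothing.

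**What to change.** Take the liver criterion out of the grade 3-4 cell. Give it its own row, or place it in a sentence above the Section 5.7 table, along these lines: *Concomitant AST/ALT 3 x ULN and bilirubin 2 x ULN requires permanent discontinuation of ATB regardless of CTCAE grade; this overrides every other row.* The wording also settles precedence over the unresolved grade 3-4 row.

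The sponsor can check the CTCAE v5 grade 2 ceilings to learn whether the overlap is real, but the edit is sound either way: if there is none, it only records the evident intent. Thresholds and the test schedule stay as they are, and no new test is needed because the mid-course panel is already planned. The cost is one row or sentence in an amendment.
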